Description of change	Several paragraphs updated and/or text added in section ' Discussion of Trial Design, including the Choice of Control Group ' to reflect the changes associated with the option to enroll additional

		
patients in existing or additional dose escalation cohorts.
 
Text added: "If deemed necessary by the Sponsor and the SMC, based on a comprehensive review of available clinical trial data, [REDACTED]
 
[REDACTED] additional patients may be enrolled after the extension cohorts into pre-existing or new dose escalation cohorts to further optimize the BI 836858 dose and determine the RP2D."

Rationale for change		See above - same as for Section 3.1
Section to be changed		3.3.3
Description of change		Exclusion criterion 9 was updated by deleting "for patients not on therapeutic vitamin K antagonists (phenprocoumon, warfarin)" to now read: Prothrombin time > 1.5 x ULN
Rationale for change		Additional information not needed as Exclusion criterion "Prothrombin time > 1.5 x ULN" applies to all patients.
Section to be changed		3.3.4.1
Description of change		Last bullet point updated with new information regarding the newly introduced first treatment on Day 8 and subsequent treatment days.
Rationale for change		Item was updated to maintain the initial logic of allowing one day of delay in starting trial treatment with BI 836858.
Section to be changed		4.1.2
Description of change		
Text added in section 'Method of assigning patients to treatment groups':
 
"In case there will be further Dose Escalation cohort(s) in the Phase I Extension part of the trial, this will be consecutive cohorts of escalating doses of BI 836858 plus decitabine, using the BLRM with overdose control. The number of patients and the decitabine schedule to be used for each cohort will be determined by the Sponsor in agreement with the SMC."

Rationale for change		See above - same as for Section 3.1
Section to be changed		4.1.3
Description of change		
New text added in section 'Selection of doses in the trial':
 
"The very first dose of BI 836858 will be split

		across two consecutive days: a fixed dose of 20 mg will be administered on Day 8 (or Day 9 at the latest) and the rest of the full planned dose for that week will be administered the following day. For example a planned dose of 80 mg will be administered as 20 mg i.v. infusion on Day 8 and 60 mg i.v. infusion on Day 9 (or 20 mg i.v. infusion on Day 9 and 60 mg i.v. infusion on Day 10 at the latest).
Rationale for change		Due to a new safety finding (fatal case of TLS) it was decided to introduce an additional safety measure by splitting the very first dose of BI 836858 (Day 8 and Day 9, or Day 9 and Day 10 at the latest).
Section to be changed		Table 4.1.3.1: 2
Description of change		
Footnote ^{a)} in Table 4.1.3.1: 2 was updated to reflect that the first administration of BI 836858 will take place on Day 8 instead of Day 9 (or on Day 9 at the latest).
 
Footnote ^{d)} in Table 4.1.3.1: 2 was updated by adding the following text:
 
“Additional Phase I Dose Escalation cohorts may also be opened if deemed necessary by the Sponsor and the SMC following the Phase I Extension cohorts of the trial.”

Rationale for change		See above - same as for Sections 3.1(for footnote d) and 4.1.3 (for foot note a)
Section to be changed		4.1.3.1
Description of change		Text added in section describing ‘ Treatment in the Phase I Dose Escalation part of the trial ’: “For the optional Dose Escalation Cohorts following Extension Cohorts A and B, a time interval of at least 3 days must have elapsed between the 1 st administration of BI 836858 for each new patient treated. This means that start of trial treatment with decitabine (Cycle 1_Day 1) for the next subsequent patient may occur at the earliest on Cycle 1_Day 4 of the previous patient.”
Rationale for change		In other trials with BI 836858 a higher dose of 160 mg has already been tested and was found to be safe. A time interval of at least 3 days between start of trial treatment in subsequent patients within one cohort is considered adequate in this setting.

Section to be changed	4.1.3.2
Description of change	Text added in section describing the treatment in the “Phase I Extension” part of the trial: “If deemed necessary by the Sponsor and the SMC, there will be an option to open further Dose Escalation cohort(s) following the extension cohorts to optimize or confirm the RP2D, based on additional biomarker, PK/PD and safety data. For further details on dose escalation procedures refer to Section 4.1.3.1 .”
Rationale for change	See above - same as for Section 3.1
Section to be changed	4.1.3.3
Description of change	The text in this section was updated to reflect that the first administration of BI 836858 will take place on Day 8 instead of Day 9 (or on Day 9 at the latest).
Rationale for change	See above - same as for Section 4.1.3
Section to be changed	4.1.4
Description of change	The text in this section was updated to reflect that the first administration of BI 836858 will take place on Day 8 instead of Day 9 (or on Day 9 at the latest).
Rationale for change	See above - same as for Section 4.1.3
Section to be changed	4.1.4.1
Description of change	Text describing the premedication was updated to reduce the obligatory premedication from the first four to only the first two administration of BI 836858. During subsequent administrations allow for flexibility of glucocorticoid dose depending on occurrence of IRR grade 2 or higher.
Rationale for change	Treatment with glucocorticoids may interfere with activity of effector-cells; in patients without IRRs during the first infusion (Day 8+9) mandatory premedication with glucocorticoid should be reduced to 50 mg for the 2 nd infusion (Day 16), and in case of good tolerability even be omitted in subsequent infusions. As this option is limited to patients with IRRs grade 1 or without IRRs, this approach is considered to offer the best possible activity to patients with the lowest risk for severe IRRs based on previous tolerability.
Section to be changed	4.2.1

Description of change	
Additional information entered as a new paragraph “Prevention and treatment of Tumor Lysis Syndrome (TLS): Risk for TLS should be assessed as per published guidelines prior to starting treatment with BI836858 (R18-1901). All patients should receive adequate hydration prior to start of each administration of BI 836858 in Cycle 1. Prophylactic administration of anti-hyperuricaemic agents (e.g. allopurinol, rasburicase) should be considered according to individual patient risk. Laboratory monitoring for TLS is mandatory as outlined in Table 1 and Section 5.3.6.1. In patients developing laboratory or clinical signs of a tumor lysis syndrome (e.g. hyperkalemia, hyperphosphatemia, hyperuricemia and hyperuricosuria, hypocalcemia, and acute renal failure), accepted treatments standards as per published recommendations must be applied (R18-1901, R10-4517).”

Rationale for change	Implemented as an urgent safety measure, as careful monitoring and early medical intervention can minimize the risk for severe TLS.
Section to be changed	4.2.2.2
Description of change	Text updated from “at least 24 h” to now “approximately 48 hours” to reflect the prolonged requirement for hospitalization in treatment Cycle 1 on Day 8 and Day 9.
Rationale for change	Due to the newly introduced treatment Day 8 in Cycle 1 and the intensive blood sampling for PK, ADA and TLS lab parameters on Day 8 and Day 9, it is required to keep trial participants as in-patients for two days (approximately 48 hours).
Section to be changed	5.3.1
Description of change	Text corrected in DL T section from “at least 2 administrations of BI 836858” to “at least 3 administrations of BI 83685” to align with corresponding text in CTP Section 3.3.4.1 .
Rationale for change	Correction of typo.
Section to be changed	5.3.3
Description of change	Text added in section describing “Recommended Phase II Dose (RP2D)” : If deemed necessary by the Sponsor and the SMC, there will be an option

Proprietary confidential information © 2019 Boehringer Ingelheim International GmbH or one or more of its affiliated companies

		to open further Dose Escalation cohort(s) following the extension cohorts to determine the RP2D, based on additional biomarker, PK/PD and safety data.
Rationale for change		Updated to reflect patients entered into the additional optional Phase I Dose Escalation cohort(s) to be recruited prior to starting the Phase II part of the trial.
Section to be changed		5.3.6.1
Description of change		Text added in section describing “ General safety laboratory parameters ” to describe the new screening for laboratory evidence of tumor lysis syndrome.
Rationale for change		Implemented as an urgent safety measure, as careful monitoring and early medical intervention can minimize the risk for severe TLS.
Section to be changed		5.3.8.1
Description of change		Tumor Lysis Syndrome (TLS) added to the AESI list.
Rationale for change		TLS added to list of AESIs to minimize risk of delayed reporting.
Section to be changed		5.5
Description of change		The text in this section was updated to reflect that the first administration of BI 836858 will take place on Day 8 instead of Day 9 (or day 9 at the latest). The reference to “[days]...of decitabine treatment” was deleted, as not all patients will receive treatment with decitabine on Day 8 and day 9.
Rationale for change		See above - same as for section 4.1.3 and correction of unclear reference.
Section to be changed		6.2.2
Description of change		The text in this section was updated to reflect that the first administration of BI 836858 will take place on Day 8 instead of Day 9 (or on Day 9 at the latest).
Rationale for change		See above - same as for Section 4.1.3
Section to be changed		7.4
Description of change		Text added in section describing “ Planned Analysis ” to describe the optional additional Dose Escalation cohort(s).
Rationale for change		Updated to reflect patients entered into the

Proprietary confidential information © 2019 Boehringer Ingelheim International GmbH or one or more of its affiliated companies

		additional optional Phase I Dose Escalation cohort(s) to be recruited prior to starting the Phase II part of the trial.
Section to be changed		7.4
Description of change		Text added in section describing “ Interim Analysis ” to describe the optional additional Dose Escalation cohort(s).
Rationale for change		Updated to reflect patients entered into the additional optional Phase I Dose Escalation cohort(s) to be recruited prior to starting the Phase II part of the trial.

Proprietary confidential information © 2019 Boehringer Ingelheim International GmbH or one or more of its affiliated companies

Number of global amendment		6
Date of CTP revision		21 Aug 2019
EudraCT number		2015-002892-30
BI Trial number		1315.2
BI Investigational Product(s)		BI 836858
Title of protocol		An open-label, Phase I/II trial to determine the maximum tolerated dose and investigate safety, pharmacokinetics and efficacy of BI 836858 in combination with decitabine in patients with acute myeloid leukemia
To be implemented only after approval of the IRB / IEC / Competent Authorities	X	
To be implemented immediately in order to eliminate hazard – IRB / IEC / Competent Authority to be notified of change with request for approval		
Can be implemented without IRB / IEC / Competent Authority approval as changes involve logistical or administrative aspects only		
Section to be changed		
After the Sponsor's decision to discontinue development of BI 836858 and to stop further recruitment of patients into study 1315.2, trial participants still on treatment and with clinical benefit from BI 836858 and decitabine are kept on treatment in this trial (as per protocol section 6.2.3.3).
 
With the aim to minimize the burden for trial participants, the mandatory protocol procedures are reduced for all patients in treatment cycles >7.
 
Changes have been made in the following sections:
 
Synopsis – section “Number of patients” Actual number of patients entered/treated in Phase I Dose Escalation (16 patients) and in Phase I Extension (33 patients) was added. One new sentence added:

		
“After completion of recruitment to Phase I Extension Cohort A and Cohort B, the recruitment to this trial is discontinued.”
 
● Flow chart: Section describing “Cycles ≥ 4” supplemented with additional information (new column) describing procedures in “Cycle >7” to reflect the assessments per visit. Clarifications added in the existing footnotes *****), 11, 12 and 13; new footnotes 19, 20 and 21 added.● 3.1 Overall Trial Design and Plan Clarification added about discontinuation of recruitment to this trial.● 3.3.4.2 Discontinuation of the trial by the Sponsor Clarification added about discontinuation of recruitment to this trial.● 5.3. Assessment of Safety Clarifications added about reduced mandatory protocol procedures for treatment cycles >7 with reference to updated Flow chart. 
New text: After completion of recruitment to Phase I Extension Cohort A and Cohort B, the recruitment to this trial is discontinued.
 
With the aim to minimize the burden for trial participants, after approval of Protocol version 7.0, the mandatory protocol procedures described below in sections 5.3.4 (Physical Examination), 5.3.6 (Safety laboratory)

--	--	---

	
parameters), 5.3.7 (Electrocardiogram), are reduced for all patients who continue to receive trial medication in treatment cycles >7. Instead, routine safety assessments should be performed at the investigator's discretion, based on standard medical care. For details refer to Flow Chart.
 
Findings are documented in the eCRF only if qualifying for an adverse event (see sections 5.3.8 and 5.3.9, unchanged).
 
5.3.5 Vital Signs New text: After implementation of Protocol version 7.0 the vital sign results will be documented in the eCRF only if qualifying for an adverse event (see sections 5.3.8 and 5.3.9, unchanged).6.2.2 Treatment period (also 6.2.2.1 and 6.2.2.2) Clarifications added about reduced mandatory protocol procedures for treatment cycles >7 with reference to updated Flow chart. New text: “With the aim to minimize the burden for trial participants, after approval of Protocol version 7.0, the mandatory protocol procedures are reduced for all patients who continue to receive trial medication in treatment cycles >7. Refer to updated Flow Chart for specific requirements during treatment period. [...] (after approval of Protocol version 7.0 BM assessments will be done at the investigator's discretion)”.6.2.3.1.1 Follow-up of Phase I Patients Clarification added about discontinuation of recruitment to this trial and no follow-up visits after completion of EoR visit.6.2.3.2 Trial completion for an individual patient Clarification added about discontinuation of recruitment to this trial.
--	---

Proprietary confidential information © 2019 Boehringer Ingelheim International GmbH or one or more of its affiliated companies

- **6.2.3.3 End of the whole trial**

Clarification added about the definition of the end of the whole trial. No follow-up visit after the last patient has had the EoR visit.

- **7.1.2 Phase I Extension**

Clarification added about discontinuation of recruitment to this trial.

APPROVAL / SIGNATURE PAGE

Document Number: c03377067

Technical Version Number: 8.0

Document Name: clinical-trial-protocol-version-07

Title: An open label, Phase I/II trial to determine the maximum tolerated dose and investigate safety, pharmacokinetics and efficacy of BI 836858 in combination with decitabine in patients with acute myeloid leukemia

Signatures (obtained electronically)

Meaning of Signature	Signed by	Date Signed
Author-Clinical Trial Leader		22 Aug 2019 14:00 CEST

2. LIST OF ABBREVIATIONS

Term	Definition / description
AE	Adverse event
AESI	Adverse events of special interest
ALKP	Alkaline phosphatase
ALT	Alkaline aminotransferase
AST	Aspartate aminotransferase
ATC classification	Anatomical, Therapeutic, Chemical classification
AUC	Area Under Curve
BI	Boehringer Ingelheim
BLRM	Bayesian logistic regression model
BSA	Body Surface Area
RPM	Report planning meeting
C _{max}	Maximum measured plasma concentration of the analyte
CL	Total plasma clearance
CR	Complete Remission
CRi	Complete Remission with incomplete marrow recovery
CT	Concomitant therapy
CTCAE	Common Terminology Criteria for Adverse Events
CTP	Clinical Trial Protocol
CTR	Clinical Trial Report
DBL	Data Base Lock
DILI	Drug Induced Liver Injury
DLT	Dose Limiting Toxicity
DMS	Data Management and Statistics
DOR	Duration of Remission
ECG	Electrocardiogram
ECOG	Eastern Cooperative Oncology Group
eDISH	Evaluation of Drug Induced Serious Hepatotoxicity
EFS	Event free survival
eCRF	Electronic case report form
ICH	International Conference on Harmonisation

Term	Definition / description
iPD	Important Protocol Deviation
IRR	Infusion Related Reaction
MedDRA	Medical Dictionary for Regulatory Activities
MQRM	Medical and Quality Review Meeting
MTD	Maximum tolerated dose
NE	Not evaluable
OR	Objective response
OS	Overall survival
PD	Progressive disease
PFS	Progression free survival
PK	Pharmacokinetics
PKS	Pharmacokinetic set
PR	Partial remission
PT	Preferred term
PV	Protocol deviation
REP	Residual effect period
REPd	Duration of residual effect period in days
RFS	Relapse free survival
RP2D	Recommended phase 2 dose
RPM	Report planning meeting
SAE	Serious adverse event
SD	Standard deviation
SOC	System organ class
SOP	Standard Operating Procedure
SS	Screened set
TCM	Trial Clinical Monitor
TF	Treatment failure
t_{\max}	Time from dosing to the maximum plasma concentration of the analyte
TOC	Table of contents
TS	Treated set

Term	Definition / description
TTF	Time to treatment failure

3. INTRODUCTION

As per ICH E9([1](#)), the purpose of this document is to provide a more technical and detailed elaboration of the principal features of the analysis described in the protocol, and to include detailed procedures for executing the statistical analysis of the primary and secondary variables and other data.

This TSAP assumes familiarity with the Clinical Trial Protocol (CTP), including Protocol Amendments. In particular, the TSAP is based on the planned analysis specification as written in CTP section 7 "Statistical Methods and Determination of Sample Size". Therefore, TSAP readers may consult the CTP for more background information on the study, e.g., on study objectives, study design and population, treatments, definition of measurements and variables, planning of sample size, randomisation. This TSAP follows the Boehringer Ingelheim (BI) internal reference ([2](#)).

This TSAP is based on the Project SAP wherever possible. Wordings like "randomisation (first administration of study treatment in non-randomised trials)" should therefore be interpreted as applicable.

Furthermore, in this combination trial the term investigational medicinal product is used for BI 836858 while combination drug denotes the backbone chemotherapy decitabine. The term trial medication is used for any of the two trial drugs.

SAS Version 9.4 or later version will be used for all analyses.

Due to company decision to stop this project, there is no Phase II subject enrollment so that Phase II analyses stated in CTP will be omitted.

4. CHANGES IN THE PLANNED ANALYSIS OF THE STUDY

Due to the decision to discontinue the development of BI865868, the enrollment was stopped after Phase I extension and Phase II part of the trial was cancelled as stated in CTP amendment 7.0. Thus there will be no data collection nor analyses for Phase II part .

5. ENDPOINTS(S)

5.1 PRIMARY ENDPOINT(S)

Phase I

The primary endpoints in the Phase I part of the trial are the maximum tolerated dose (MTD) and the number of subjects with of dose limiting toxicity (DLT) during the MTD evaluation period.

Maximum tolerated dose (MTD):

The MTD is defined as the highest dose of BI 836858 (in combination with decitabine) with less than 25% risk of the true DLT rate being above 33% during the MTD evaluation period.

MTD evaluation period:

The MTD evaluation period is defined as the time from the first administration of study drug to the start of the second treatment cycle or the end of 30-day residual effect period after last administration of study drug, whichever comes first. Subjects who were replaced during the MTD evaluation period will not be considered for MTD determination. The subjects who are completed the MTD evaluation period without being replaced are considered MTD evaluable.

In case a subject has not completed the required number of administrations due to BI 836858 related toxicity, he/she will not be replaced and this will be considered as DLT. However, subjects who have not completed the required number of administrations of BI 836858 for reasons other than BI 836858 related toxicity will be replaced. Subjects who were replaced during the MTD evaluation period will not be considered for MTD

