2.2 TRIAL OBJECTIVES

The objective of the present trial is to investigate BI 836858 in combination with decitabine. If justified by safety and efficacy data of BI 836858 in combination with decitabine, late phase development of BI 836858 in combination with decitabine may be considered in the future.

The trial will be performed in two parts: a Phase I part consisting of a dose escalation and an extension part, as well as a randomized Phase II part (see also [Figures 3.1.1](#) and [3.1.2](#)).

The objectives of the Phase I Dose Escalation part of the trial are to determine the MTD and to investigate safety, pharmacokinetics and efficacy of BI 836858 in combination with decitabine in previously untreated patients ≥ 65 years of age and considered ineligible for standard intensive therapy, or patients ≥ 18 years of age with relapsed or refractory AML. In case the MTD would not be reached because of preliminary signals of activity or due to tolerability issues in repeated treatment cycles at doses below the MTD, the dose to be used for further development of BI 836858 in combination with decitabine in adult patients with AML would be determined (also see [Section 3.1](#)). Within the context of this trial that dose will be referred to as the Recommended Extension Phase I Dose (RExP1D).

The objectives of the Phase I Extension cohorts are to collect additional data on safety, pharmacokinetics and efficacy and to decide if the RExP1D will become the Recommended Phase II Dose (RP2D) of BI 836858 in combination with decitabine in patients ≥ 65 years of age, or if additional patients need to be enrolled in existing or additional dose escalation cohorts. Furthermore, based on the totality of efficacy and safety data, the treatment duration of decitabine in the combination treatment with BI 836858 will be assessed for the subsequent use in the Phase II part.

In the randomized Phase II part, the primary objective is to investigate the efficacy, safety and pharmacokinetics of BI 836858 in combination with decitabine compared to decitabine monotherapy in previously untreated patients with AML, who are ≥ 65 years of age and considered ineligible for standard intensive therapy.

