5.3.3 Recommended Phase II Dose (RP2D)

Before the conclusion of Phase I and prior to initiating the Phase II, up to 30 patients will receive the combination treatment of BI 836858 at MTD (or RExP1D if applicable) and decitabine in one of the two extension cohorts.

If deemed necessary by the Sponsor and the SMC, there will be an option to open further Dose Escalation cohort(s) following the extension cohorts to determine the RP2D, based on additional biomarker, PK/PD and safety data.

Based on the overall Phase I data, the SMC will make a final determination of the RP2D, which must not exceed the MTD. The Phase I safety analysis report or lean interim CTR, including the rationale of RP2D determination will be sent to competent authorities/ethic committees and made available to all participating Investigators prior to the initiation of Phase II.

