Proprietary confidential information © 2019 Boehringer Ingelheim International GmbH or one or more of its affiliated companies

The prior distributions for θ_k ($k=1,2$) will be specified as a mixture of two bivariate normal distributions,

$$f(\theta_k) = a_{1,k} f_1(\theta_k) + a_{2,k} f_2(\theta_k)$$

with $a_{1,k}, a_{2,k}$ the prior mixture weights ($a_{1,k} + a_{2,k} = 1$) and

$f_i(\theta_k) = \text{MVN}(\mu_{ik}, \Sigma_{ik})$ ($i=1,2$) a bivariate normal distribution with mean vector μ_{ik} and covariance matrix Σ_{ik} where

$$\Sigma_{ik} = \begin{pmatrix} \sigma_{ik,11}^2 & \sigma_{ik,11}\sigma_{ik,22}\rho_{ik} \\ \sigma_{ik,11}\sigma_{ik,22}\rho_{ik} & \sigma_{ik,22}^2 \end{pmatrix}$$

Mixture prior distributions have the advantage that they allow for specification of different logistic dose-toxicity curves, therefore making the prior more robust.

A weakly-informative normal prior distribution will be used for η .

The estimated probability of DLT at each dose level from the model will be summarized using the following intervals:

Under dosing: [0.00, 0.16)

Targeted dosing: [0.16, 0.33)

Over dosing: [0.33, 1.00]

The BLRM-recommended dose for the next cohort is the level at which the probability for the target dosing interval is maximal out of the dose candidates satisfying the overdose control criterion: $P(\text{over dosing}) < 25\%$.

However, the maximum allowable dose increment for the subsequent cohort will be no more than 100% of previous dose levels.

The MTD may be considered reached if the following criteria are fulfilled:

1. The posterior probability of the true DLT rate in the target interval [0.16, 0.33] of the MTD is above 0.50, OR
2. At least 15 patients have been treated in the study, of which at least 6 were treated at the MTD.

The SMC may recommend stopping the dose finding phase after the criterion for MTD is fulfilled. Further patients may be included to confirm the MTD. If no DLT is observed at a dose of which the efficacy is considered sufficient, the SMC may decide to include additional patients at this dose level and to declare this dose as the RExP1D.

Prior derivation

To determine the prior distributions for $(\log(\alpha_1), \log(\beta_1))$ and $(\log(\alpha_2), \log(\beta_2))$, a meta-analytic predictive (MAP) approach will be used. For BI 836858 toxicity information from the ongoing 1315.1 Phase I study will be used. For decitabine toxicity information from three

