7.3.1 Primary endpoint analyses

Phase I:

In order to estimate the MTD, the occurrence of a DLT in the first treatment cycle will be assessed on an individual patient level. However, for those patients who receive more than one cycle of the combination treatment, all AEs that constitute a DLT will be considered for re-estimation of the MTD based on the BLRM. To obtain this, the model will be re-run including the DLT information from all cycles. Based on both MTD estimates, the recommended dose for the extension cohort (and the Phase II part) will be determined. The MTD will be determined using the BLRM as described in Section 7.1.1. The number of DLTs at each dose level will be presented (all cycles and first cycle separately).

Phase II:

Objective response (CR+CRi) will be analyzed descriptively in terms of objective response rate (ORR), defined as the proportion of patients with complete response (CR) or complete response with incomplete blood count recovery (CRi).

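### SAP 5.1 defines the MTD as the highest dose that passes the overdose limit, without tying it to doses given in the trial or to the protocol's criteria for the MTD being reached

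*SAP*

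**What the plan says.** SAP 5.1 defines the MTD as "the highest dose of BI 836858 (in combination with decitabine) with less than 25% risk of the true DLT rate being above 33" per cent during the MTD evaluation period. SAP 7.4 says which subjects and DLTs feed the determination, but names no model, no selection rule and no criterion for when an MTD has been established. SAP 4 declares one change only, the cancellation of Phase II. SAP 3 states in general terms that the SAP builds on Protocol section 7.

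The protocol contains no such definition in its visible text. Section 5.3.2 says which DLTs are used and points to section 7.1. Section 7.3.1 says: "The MTD will be determined using the BLRM as described in Section 7.1.1". In section 7.1.1 the limit P(overdose) < 25% decides which doses are admissible. The section then adds: "The MTD may be considered reached if the following criteria are fulfilled". The criteria are alternatives:

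- the posterior probability of the target interval at the MTD is above 0.50; or
- "At least 15 patients have been treated in the study, of which at least 6 were treated at the MTD".

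The protocol also provides for ending without an MTD. Section 2.2 begins: "In case the MTD would not be reached because of preliminary signals of activity or due to tolerability issues", and a dose called the RExP1D is then determined. Section 7.1.1 lets the SMC, where no DLT is seen at a dose considered efficacious enough, "decide to include additional patients at this dose level and to declare this dose as the RExP1D". SAP 5.1 and 7.4 mention neither the criteria nor a not-reached result, and the visible SAP text does not mention the RExP1D.

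**The concern.** The 25% and 33% figures are the protocol's own. What is new is turning an admissibility limit into the definition of a primary endpoint. A limit of that kind says a dose is not shown to be too toxic. It does not say that the dose was studied or that its DLT rate is known well enough to be called the MTD. The protocol's criteria supply that second part, through a demand on the posterior or on patient numbers at the dose.

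Without them, two things can go wrong in the report. A dose that nobody received can be named the MTD by extrapolation from the model. And a trial with few DLTs, which the protocol would allow to end with an RExP1D and no MTD, can still be reported as having found one. Phase I is now the whole trial, so this endpoint is a main result.

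**Working it through.** **Inputs.** Model and reference doses (160 mg, 20 mg/m²) from Protocol 7.1.1; priors from Table 7.1.1: 3; intervals from 7.1.1 (target 0.16 to 0.33, overdose 0.33 and above); scenarios from Table 10.2: 1. Decitabine is at its reference dose throughout.

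**Formulas.**

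- logit p1 = log α1 + β1·log(d/160); logit p2 = log α2
- p0 = p1 + p2 − p1·p2
- odds(p) = odds(p0)·exp(η·d/160)
- Draws from the prior are weighted by the binomial likelihood of the scenario. P(TD) and P(OD) are the weighted shares in the target and overdose intervals.

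**Step 1: reproduce the protocol's figures.** Prior P(OD), 4,000,000 draws:

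| Dose (mg) | 20 | 40 | 80 | 160 | 320 |
|---|---|---|---|---|---|
| Printed (Table 7.1.1: 4) | 0.133 | 0.186 | 0.312 | 0.537 | 0.665 |
| Recomputed | 0.135 | 0.190 | 0.312 | 0.538 | 0.670 |

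Scenario 12 at 240 mg, P(underdose)/P(TD)/P(OD): printed 0.587/0.203/0.210, recomputed 0.592/0.201/0.207. The model is reproduced closely enough.

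**Step 2: the SAP sentence with no data.** From the printed prior, 40 mg passes (0.186 < 0.25) and 80 mg does not (0.312). Of the listed doses, the definition names 40 mg before any patient is treated.

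**Step 3: scenario 12**, 0/3 DLTs at each of 20, 40, 80 and 160 mg. At 240 mg, P(OD) = 0.210 < 0.25; at 320 mg the recomputed value is 0.281, which fails. On these doses the SAP sentence names 240 mg.

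- Criterion 1: P(TD) = 0.203, not above 0.50.
- Criterion 2: 3 + 3 + 3 + 3 = 12 patients, fewer than 15; patients at 240 mg = 0, fewer than 6.

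Neither is met.

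**Step 4: 16 patients without a DLT.** Sixteen is the actual escalation number (Protocol Synopsis). The absence of DLTs and the splits over doses are assumptions.

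- 3, 3 and 10 patients at 20, 40 and 80 mg: 160 mg has P(OD) about 0.16, so it passes. No patient received it and its P(TD) is about 0.22, so neither criterion is met there. Criterion 2 could be met at 80 mg (16 ≥ 15 and 10 ≥ 6).
- 3, 3, 3, 4 and 3 patients at 20, 40, 80, 160 and 320 mg: 320 mg has P(underdose) 0.847, P(TD) 0.116 and P(OD) 0.037. It passes with 3 patients, and no dose meets either criterion. If doses not given count, 640 mg also passes (P(OD) 0.100).

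The sentence names no dose list, so nothing in it stops the extrapolation.

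**Step 5: how often.** Approximate simulation: 2000 trials for each of the four truths in Table 10.2: 2, cohorts of 3, doses 20 to 320 mg, read at 15 patients, trials with no admissible dose excluded. If doses not given count, the SAP sentence names such a dose, with neither criterion met, in 3.3% to 17.8% of trials. These figures are good to a few percentage points only. Restricted to doses given, it never named a dose that met neither criterion. The second split in step 4 shows that this can still happen.

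**The case against.** The strongest defence is that the protocol has no rival definition. Its criteria are permissive, inform the SMC's decision to stop, and speak of the MTD as a dose already identified. SAP 5.1 then supplies the missing definition from the protocol's own overdose limit. Other text fits: Protocol 5.3.3 treats the MTD as a ceiling ("the SMC will make a final determination of the RP2D, which must not exceed the MTD"), and 7.1.2 checks the RP2D against the overdose limit. This stands as far as it goes: the SAP wording is a possible elaboration, and a flat contradiction is not shown. It does not explain why the criteria and the not-reached outcome drop out of the section that defines the endpoint.

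SAP 3 may import Protocol section 7, criteria included. That is possible, but a general reference does not settle which text governs once the SAP writes its own explicit definition. Likewise, Protocol 3.1 describes estimating DLT probabilities for dose levels in the study, which suggests that doses never given were not intended. SAP 5.1 does not say so. Scenario 12 is also a mid-escalation picture; it shows what the sentence does and does not predict this trial.

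Two stronger readings are tempting. A reader might infer that the protocol defines the MTD as the admissible dose with the largest target probability, so that the SAP contradicts it. The rule is worded otherwise: "The BLRM-recommended dose for the next cohort is the level at which the probability for the target dosing interval is maximal". It guides the next cohort and is no definition of the MTD. A reader might also infer that failing both criteria means the MTD was not reached. Protocol 2.2 ties that outcome to activity signals or tolerability in repeated cycles, and 7.1.1 says only when the MTD may be considered reached.

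**Conclusion.** The concern holds in limited form. Read literally, SAP 5.1 returns an MTD whenever any dose passes the overdose limit. It can name a dose that no patient received and that meets neither protocol criterion, as printed scenario 12 shows, and it allows no not-reached result unless no dose passes. Most of the problem disappears if the definition is limited to doses given; the question of a not-reached result remains.

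The figures rest on the Table 7.1.1: 3 priors, which Protocol 7.1.1 allows to be updated, and on assumed patient splits. Parts of the SAP are blacked out, so silence can be judged only for the visible text; sections 5.1 and 7.4 are visible. It might be inferred that the trial's reported MTD is wrong. The documents do not support that: the dose levels in the escalation scheme are blacked out and no DLT counts are given, so the effect on the actual result is unknown. With Phase II cancelled, the consequence is confined to what is reported as the MTD. It should still be fixed, because the MTD is a primary endpoint.

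**What to change.** Reconcile SAP 5.1 and 7.4 with Protocol 7.1.1 and 2.2, so that the reported MTD is tied to the doses studied and to the protocol's criteria for the MTD being reached. List MTD not reached, together with the RExP1D if one was declared, as a reportable result. If the SAP definition is meant to replace the protocol's criteria, declare that in SAP 4 as a change, with the reason.

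The cost is one SAP paragraph; the existing model is reused. The report may then have to state that the MTD was not reached. No dose is proposed here.
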